17. PREMATURE TERMINATION OF THE STUDY OR CLOSE-OUT OF A SITE

17.1. Premature Termination of the Study

The sponsor has the right to terminate the study prematurely. Reasons may include efficacy, safety, or futility, among others. Should the sponsor decide to terminate the study, the investigator(s) will be notified in writing.

17.2. Close-out of a Site

The sponsor and the investigator have the right to close-out a site prematurely.

Investigator's Decision

The investigator must notify the sponsor of a desire to close-out a site in writing, providing at least 30 days' notice. The final decision should be made through mutual agreement with the sponsor. Both parties will arrange the close-out procedures after review and consultation.

Sponsor's Decision

The sponsor will notify the investigator(s) of a decision to close-out a study site in writing. Reasons may include the following, among others:

- The investigator has received all items and information necessary to perform the study, but has not enrolled any patient within a reasonable period of time
- The investigator has violated any fundamental obligation in the study agreement, including but not limited to, breach of this protocol (and any applicable amendments), breach of the applicable laws and regulations, or breach of any applicable ICH guidelines
- The total number of patients required for the study are enrolled earlier than expected

In all cases, the appropriate IRB/EC and Health Authorities must be informed according to applicable regulatory requirements, and adequate consideration must be given to the protection of the patients' interests.

18. STUDY DOCUMENTATION

18.1. Certification of Accuracy of Data

A declaration assuring the accuracy and content of the data recorded on the CRF/eCRF must be signed electronically by the investigator. This signed declaration accompanies each set of patient final CRF/eCRF that will be provided to the sponsor.

18.2. Retention of Records

The investigator must retain all essential study documents, including ICFs, source documents, investigator copies of CRFs, and drug accountability records for at least 15 years following the completion or discontinuation of the study, or longer, if a longer period is required by relevant

regulatory authorities. The investigator must obtain written approval from the sponsor before discarding or destroying any essential study documents during the retention period following study completion or discontinuation. Records must be destroyed in a manner that ensures confidentiality.

If the investigator's personal situation is such that archiving can no longer be ensured, the investigator must inform the sponsor (written notification) and the relevant records will be transferred to a mutually agreed-upon destination.

19. DATA QUALITY ASSURANCE

In accordance with ICH E6, the sponsor is responsible for quality assurance to ensure that the study is conducted and the data generated, recorded, and reported in compliance with the protocol, GCP, and any applicable regulatory requirement(s). The planned quality assurance and quality control procedures for the study are summarized.

Data Management

The sponsor is responsible for the data management of this study including quality checking of the data (Section 12.1.1).

Study Monitoring

The investigator must allow study-related monitoring, IRB/EC review, audits, and inspections from relevant health regulatory authorities, and provide direct access to source data documents (Section 13.1, Section 13.2, Section 14).

The study monitors will perform ongoing source data review to verify that data recorded in the CRF by authorized site personnel are accurate, complete, and verifiable from source documents, that the safety and rights of patients are being protected, and that the study is being conducted in accordance with the current approved protocol version and any other study agreements, ICH GCP, and all applicable regulatory requirements (Section 13.1).

All patient data collected during the study will be recorded on paper or electronic CRF unless the data are transmitted to the sponsor or designee electronically (eg, laboratory data). The investigator is responsible for affirming that data entries in the CRF are accurate and correct by electronically signing a declaration that accompanies each set of patient final CRF (Section 13.3 and Section 18.1).

Study Documentation

The investigator must maintain accurate documentation (source data) that supports the information entered in the CRF (Section 13.2).

The investigator will retain all records and documents, including signed ICFs, pertaining to the conduct of this study for at least 15 years after study completion, unless local regulations or institutional policies require a longer retention period. No records may be destroyed during the retention period without the written approval of the sponsor. No records may be transferred to another location or party without written notification to the sponsor (Section 18.2).

20. CONFIDENTIALITY

Confidentiality of information is provided as a separate agreement.

21. FINANCING AND INSURANCE

Financing and insurance information is provided as a separate agreement.

22. PUBLICATION POLICY

The publication policy is provided as a separate agreement.

24. INVESTIGATOR’S AGREEMENT

I have read the attached protocol: “A Study to Evaluate the Efficacy and Safety of Dupilumab Monotherapy in Pediatric Patients with Peanut Allergy” and agree to abide by all provisions set forth therein.

I agree to comply with the current International Council for Harmonisation Guideline for Good Clinical Practice and the laws, rules, regulations, and guidelines of the community, country, state, or locality relating to the conduct of the clinical study.

I also agree that persons debarred from conducting or working on clinical studies by any court or regulatory agency will not be allowed to conduct or work on studies for the sponsor or a partnership in which the sponsor is involved. I will immediately disclose it in writing to the sponsor if any person who is involved in the study is debarred, or if any proceeding for debarment is pending, or, to the best of my knowledge, threatened.

This document contains confidential information of the sponsor, which must not be disclosed to anyone other than the recipient study staff and members of the IRB/EC. I agree to ensure that this information will not be used for any purpose other than the evaluation or conduct of the clinical investigation without the prior written consent of the sponsor.

(Signature of Investigator)

(Date)

(Printed Name)

APPENDIX 1. PEANUT DBPCFC SCHEDULE OF DOSING PERFORMED AT SCREENING AND WEEKS 24 AND 36

	Challenge Doses			
	Amount of Peanut Protein at Each Challenge Dose (mg)	Amount of Peanut Flour with 50% Protein Content (mg)	Cumulative Amount of Peanut Protein (mg) at Screening	Cumulative Amount of Peanut Protein (mg) on Study (Weeks 24 and 36)
Screening	1	2	1	1
Screening	3	6	4	4
Screening	10	20	14	14
Screening	30	60	44	44
Screening	100	200	144	144
Endpoint	300	600	-	444
Endpoint	600	1200	-	1044
Endpoint	1000	2000	-	2044

Note: The DBPCFC is to be conducted as 2 challenges, each on a separate day using a placebo (artificially peanut-flavored oat protein) for one challenge and peanut (as defatted peanut protein) for the other. The oral food challenge is to be performed under double-blind conditions so that neither the patient, nor the patient's caregiver, nor any of the clinic staff (save for the unblinded preparer of the challenge foods) knows which challenge contains the peanut or the placebo. The clinic staff may not be unblinded as to the order of the 2 parts (peanut and placebo) of the DBPCFC until after completion of the observation period of the second part of the challenge for the screening challenge only. For weeks 24 and 36, the study team will remain blinded to the order of the exposure for each challenge date.

APPENDIX 2. ALLERGY REACTION SEVERITY GRADING

The Consortium of Food Allergy Research (CoFAR) grading system for allergic reactions

Grade 1 - Mild	Grade 2 - Moderate	Grade 3 – Severe	Grade 4 - Life Threatening	Grade 5 – Death
Transient or mild discomforts (< 48 hours), no or minimal medical intervention/therapy required. These symptoms may include pruritus, swelling or rash, abdominal discomfort or other transient symptoms.	Symptoms that produce mild to moderate limitation in activity some assistance may be needed; no or minimal intervention/therapy is required. Hospitalization is possible. These symptoms may include persistent hives, wheezing without dyspnea, abdominal discomfort/ increased vomiting or other symptoms	Marked limitation in activity, some assistance usually required; medical intervention/therapy required, hospitalization is possible Symptoms may include Bronchospasm with dyspnea, severe abdominal pain, throat tightness with hoarseness, transient hypotension among others. Parenteral medication(s) are usually indicated.	Extreme limitation in activity, significant assistance required; significant medical/therapy. Intervention is required; hospitalization is probable. Symptoms may include persistent hypotension and/or hypoxia with resultant decreased level of consciousness associated with collapse and/or incontinence or other life-threatening symptoms.	Death

PRACTALL consensus report on DBPCFC, and with the CoFAR grading system for allergic reactions, are provided as a general guide.

Mild Symptoms:

- Skin – limited (few) or localized hives, swelling (eg, mild lip edema), skin flushing (eg, few areas of faint erythema) or pruritus (mild, eg, causing occasional scratching)
- Respiratory – rhinorrhea (eg, occasional sniffing or sneezing), nasal congestion, occasional cough, throat discomfort
- Gastrointestinal (GI) – mild abdominal discomfort (including mild nausea), minor vomiting (typically a single episode) and/or a single episode of diarrhea

Moderate Symptoms:

- Skin – systemic hives (eg, numerous or widespread hives), swelling (eg, significant lip or face edema), pruritus causing protracted scratching, more than a few areas of erythema or pronounced erythema
 - Respiratory – throat tightness without hoarseness, persistent cough, wheezing without dyspnea
- GI – persistent moderate abdominal pain/cramping/nausea, more than a single episode of vomiting and/or diarrhea

Severe Symptoms:

- Skin – severe generalized urticaria/angioedema/erythema
- Respiratory – laryngeal edema, throat tightness with hoarseness, wheezing with dyspnea, stridor
 - GI – severe abdominal pain/cramping/repetitive vomiting and/or diarrhea
 - Neurological – change in mental status
 - Circulatory – clinically significant hypotension

APPENDIX 3. CRITERIA FOR SUSPECTED DIAGNOSIS AND SEVERITY GRADING OF ANAPHYLAXIS

Anaphylaxis is likely when any 1 of the 3 following sets of criteria is fulfilled:

1. Acute onset of an illness (minutes to hours) with involvement of:
 - Skin/mucosal tissue (eg, generalized hives, itch or flush, swollen lips/tongue/uvula) AND
 - Airway compromise (eg, dyspnea, stridor, wheeze/ bronchospasm, hypoxia, reduced PEF) AND/OR
 - Reduced BP or associated symptoms (eg, hypotonia, syncope, incontinence)
2. Two or more of the following that occur rapidly after exposure to the allergen (minutes to hours):
 - Skin/mucosal tissue (eg, generalized hives, itch/flush, swollen lips/tongue/uvula)
 - Airway compromise (eg, dyspnea, stridor wheeze/bronchospasm, hypoxia, reduced PEF)
 - Reduced BP or associated symptoms (eg, hypotonia, syncope, incontinence)
 - Persistent GI symptoms (eg, nausea, vomiting, crampy abdominal pain)
3. Reduced BP after exposure to the allergen (minutes to hours):
 - Infants and Children: low systolic BP (age-specific) or >30% drop in systolic BP*
 - Adults: systolic BP <90 mm Hg or >30% drop from their baseline

* Low systolic BP for children is defined as <70 mm Hg from 1 month to 1 year; less than (70 mm Hg + [2 x age]) from 1 to 10 years; and <90 mm Hg from age 11 to 17 years.

Note: Isolated skin or mucosal lesions following the ingestion of a food constitute a “food-induced allergic reaction”.

Criteria for Severity Grading (Muraro 2007)

Staging System of Severity of Anaphylaxis	
Stage	Defined By
1. Mild (skin & subcutaneous tissues, GI, &/or mild respiratory)	Flushing, urticaria, periorbital or facial angioedema; mild dyspnea, wheeze or upper respiratory symptoms; mild abdominal pain and/or emesis
2. Moderate (mild symptoms + features suggesting moderate respiratory, cardiovascular or GI symptoms)	Marked dysphagia, hoarseness and/or stridor; shortness of breath, wheezing & retractions; crampy abdominal pain, recurrent vomiting and/or diarrhea; and/or mild dizziness
3. Severe (hypoxia, hypotension, or neurological compromise)	Cyanosis or SpO ₂ ≤92% at any stage, hypotension, confusion, collapse, loss of consciousness; or incontinence

SIGNATURE OF SPONSOR’S RESPONSIBLE OFFICERS

(Medical/Study Director, Regulatory Representative, Clinical Study Team Lead, and Biostatistician)

To the best of my knowledge, this report accurately describes the conduct of the study.

HBsAg Hepatitis B surface antigen

Hep C Ab Hepatitis C antibody

HIV Human immunodeficiency virus

ICF Informed consent form

ICH International Council for Harmonisation

IgE Immunoglobulin E

IL-4 Interleukin 4

IL-4Rα Interleukin 4 Receptor Alpha

IL-13 Interleukin 13IM IntramuscularIL Interleukin

IRB Institutional Review Board

Regeneron Pharmaceuticals, Inc. Statistical Analysis Plan

IV Intravenous

LDH Lactate dehydrogenase

MedDRA Medical Dictionary for Regulatory Activities

NAb Neutralizing antibody
OIT Oral immunotherapy

PBMC Peripheral blood mononuclear cells
PCSV Potentially clinically significant value

PEFR/PEF Peak expiratory flow rate

PK Pharmacokinetic
POC Proof-of-concept
PT Preferred term
Q2W Every 2 weeks
RBC Red blood cell

Regeneron Pharmaceuticals, Inc.

SAE Serious adverse event
SAF Safety analysis set
SAP Statistical analysis plan

SAS Statistical Analysis System

SC Subcutaneous

sIgE Peanut-specific IgE SOC System organ class SPT Skin prick test

SUSAR Suspected unexpected serious adverse reaction

TEAE Treatment-emergent adverse event

ULN Upper limit of normal

WBC White blood cell

Protocol: R668-ALG-1702

Date: March 3, 2021

1. **OVERVIEW**

The purpose of the statistical analysis plan (SAP) is to ensure the credibility of the study results by pre-specifying the statistical approaches for the analysis of study data prior to database lock. The SAP is intended to be a comprehensive and detailed description of the strategy and statistical methods to be used in the analysis of data for R668-ALG-1702 study.

Protocol: R668-ALG-1702

Date: March 3, 2021

This plan may be revised during the study to accommodate protocol amendments and/or to make changes to adapt to unexpected issues in study execution and/or data that affect planned analyses. These revisions will be based on review of the study and data, and a final plan will be issued prior to data lock.

1.1. Background/Rationale

Food allergy is a potentially life-threatening condition that affects up to 8% of young children and 3% to 5% of the entire United States (US) population (Gupta, 2011) (Sicherer, 2010) (Nwaru, 2014). Unlike many other childhood allergies, peanut allergy typically persists into adulthood and is associated with a higher incidence of severe anaphylaxis as compared with other food allergies (Dyer, 2015). The prevalence of peanut allergy by self-reports in US and European Union (EU) children varies from 1.2% to 2.0% (Dunlop, 2018). The current remedies for food allergy are food avoidance and treatment with medications such as injectable epinephrine for accidental exposures associated with severe allergic symptoms. Although recent progress has been made in the treatment of food allergy through allergen-specific oral immunotherapy (OIT), there is an unmet need for a new therapy in food allergy. (Jones, 2009) (Anagnostou, 2011) (Anagnostou, 2014). The aim of oral immunotherapy (OIT) is to induce desensitization and increase the threshold for peanut ingestion and reduce the risks of allergic reactions after accidental ingestion. However, many subjects in OIT trials continue to have side effects that can hinder their compliance and the overall efficacy of OIT. There is also a subsequent rapid loss of tolerance upon cessation of OIT (Vickery, 2014) (Wood, 2017).

The immune system in the gut actively induces an immune tolerant state to the proteins that are normally consumed. Food allergy occurs when the body has a break in this tolerance, which results in an abnormal immune reaction to food. It is known that allergic response to food including peanut protein is an immunoglobulin E (IgE) mediated event; however, recent data suggest that interleukin (IL-4) and IL-13 may also play a significant role in food allergy pathogenesis.

Dupilumab, a fully human VelocImmune-derived monoclonal antibody directed against interleukin-4 receptor alpha (IL-4R α), blocks the activity of IL-4 and IL-13 and is approved as a treatment for atopic dermatitis (AD).

This phase 2 proof-of-concept (POC) study will explore whether dupilumab has immunomodulatory effects on type 2 immune responses, which may result in improved safety and tolerance to peanut exposure as determined by the ability to tolerate a higher cumulative peanut protein dose level during a double-blind, placebo-controlled food challenge (DBPCFC) after 24 weeks of monotherapy treatment. In addition, the study will evaluate whether dupilumab influences known biomarkers that are important in the allergic response to peanuts such as a reduction in allergen-specific IgE and/or increase in allergen-specific IgG4.

1.2. Study Objectives

1.2.1. Primary Objectives

The primary objective of this study is to assess the tolerability of peanut protein in pediatric patients (6 ot 17 years old) treated with dupilumab monotherapy, in which tolerability is defined as the proportion of patients who safely pass a double-blinded placebo-controlled food challenge (DBPCFC) at week 24.

Protocol: R668-ALG-1702

Date: March 3, 2021

1.2.2. Secondary Objectives

The secondary objectives of the study include:

- To determine whether dupilumab treatment improves peanut tolerability, defined as a change in the cumulative tolerated dose (log transformed) of peanut protein during a DBPCFC (up to 2044 mg cumulative)
- To evaluate the safety and tolerability of dupilumab treatment in peanut allergic patients
- To evaluate the effects of dupilumab treatment on the levels of peanut-specific IgE, IgG, IgG4 and peanut-specific IgG4/sIgE ratio, and peanut-specific IgG/sIgE ratio
- To evaluate the treatment effect of dupilumab on the average wheal size after a titrated skin prick test (SPT), as measured by area under the curve (AUC) of the average wheal size induced by peanut extract at different concentrations
- To assess the incidence of treatment-emergent anti-drug antibodies (ADA) to dupilumab in patients over time

1.2.3. Modifications from the Statistical Section in the Final Protocol

Modifications from protocol amendment 2:

- Removed the FAS and week 36 FAS for efficacy analysis. This study design is an openlabel, single-arm study, and all patients receive study drug treatment. The SAF includes all patients who received any dupilumab that can be applied to either safety or efficacy endpoint; Also, the efficacy analyses at week 36 are based on SAF for patients who pass a DBPCFC of at least 444 mg (cumulative) of peanut challenge at week 24.
- The primary analysis for primary and secondary endpoints will be analyzed using descriptive statistics instead of inferential statistics. Therfore, the p-value stated in the protocol will be removed from analysis.

1.2.4. Revision History for SAP Amendments

NA

2. INVESTIGATION PLAN

2.1. Study Design and Randomization

This is a phase 2, multicenter, single-arm open-label POC study in pediatric patients aged 6 to 17 years inclusive who are allergic to peanut, to evaluate the effects of dupilumab on tolerability of peanut protein during a DBPCFC.

Protocol: R668-ALG-1702

Date: March 3, 2021

2.2. Statistical Hypothesis

The statistical hypothesis is on the primary endpoint, the proportion of patients who achieve a cumulative dose of at least 444 mg peanut protein during a DBPCFC at week 24.

Let μ_D be the true proportion of patients who achieve a cumulative dose of 444 mg peanut protein during a DBPCFC at week 24 for dupilumab. The following hypothesis will be tested at the 2-sided 5% significance level:

Null hypothesis H_0 : $\mu_D = 8\%$, ie, the proportion of patients who achieve a cumulative dose of 444 mg peanut protein during a DBPCFC at week 24 is 8% (Vickery, 2018).

Alternative hypothesis H_a : $\mu_D \neq 8\%$, ie, the proportion of patients who achieve a cumulative dose of 444 mg peanut protein during a DBPCFC at week 24 is different from 8%.

2.3. Sample Size and Power Considerations

The sample size is determined to adequately power the primary endpoint of the proportion of patients who pass at least a DBPCFC of 444 mg (cumulative) of peanut protein at week 24. Based on assessment of clinical data from Aimmune Therapeutics AR101 phase 3 peanut OIT study (ARC003), it is assumed that the rate of a tolerated cumulative dose of at least 444 mg of peanut protein on DBPCFC at week 24 is 8% in placebo (Vickery, 2018) and 29% in dupilumab.

A sample size of 20 patients will have 80% power to detect the 21% difference in tolerated rate at the 2-sided 5% significance level. Allowing for a dropout rate of around 15%, approximately 24 patients will be required. The sample size calculations were done by one-sample Chi-square test (normal approximation) using nQuery + nTerim 4.

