11.2. Justification of Sample Size

The sample size is determined to adequately power the primary endpoint of the proportion of patients who pass at least a DBPCFC of at least 444 mg (cumulative) of peanut protein at week 24. Based on assessment of clinical data from the Aimmune Therapeutics AR101 phase 3 study, it is assumed that the rate of a tolerated cumulative dose of at least 444 mg of peanut protein on DBPCFC at week 24 is 29% in dupilumab and 8% in placebo (Vickery, 2018).

A sample size of 20 patients will have 80% power to detect the 29% tolerated rate in dupilumab group at the 2-sided 5% significance level. Allowing for a dropout rate of around 15%, approximately 24 patients will be required. The sample size calculations were done by one-sample Chi-square test (normal approximation) using nQuery + nTerim 4.

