11.4.3.1. Primary Efficacy Analysis

The FAS will be used for the primary efficacy endpoint. The primary endpoint will be analyzed using one-sample Chi-square test. Estimate of proportion, p-value, and the 2-sided 95% confidence interval will be provided.

If a patient does not have available DBPCFC data at week 24, the patient will be considered as a non-responder regardless of reasons for missing data.

Sensitivity analyses of the primary endpoint will include an analysis of the subset of patients with available week 24 DBPCFC. Other sensitivity analyses may be proposed in the SAP.

Subgroup analysis (eg, by baseline weight group) will be performed.

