5.6.1. Analysis of Primary Efficacy Variable

The primary endpoint will be analyzed using descriptive statistics. Estimate of proportion and the 2-sided 95% Clopper-Pearson confidence interval will be provided. The number and percentage of patients at each dose level for highest tolerated peanut protein dose at week 24 DBPCFC will also be summarized.

Missing data for week 24 DBPCFC will be handled according to the reason for missingness as follows:

- If a patient misses the week 24 DBPCFC due to COVID-19, the missing data will be imputed by multiple imputation (MI) method for 10 times utilizing available week 24 DBPCFC data. The MI will utilize logistic regression method with baseline tolerated cumulative amount of peanut protein DBPCFC.
- If a patient does not have available DBPCFC data at week 24 due to reasons not related to COVID-19, the patient will be considered as a non-responder at week 24.

Each of complete datasets after the above steps will be summarized with estimated proportions and standard errors. The SAS MIANALYZE procedure will be used to generate valid statistical inferences by combining results using Rubin's formula (Rubin, 1987).

Supportive analysis of the primary endpoint will include an analysis of patients who have available week 24 DBPCFC of peanut protein.

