10. APPENDIX

10.1. Summary of Statistical Analyses

Efficacy Analysis:

Endpoint	Analysis Populations	Primary Statistical Method	Supportive/Sensitivity Analysis	Subgroup Analysis	Other Analyses
Primary Endpoint					•
Proportion of patients treated with dupilumab that pass a DBPCFC with at least 444 mg (cumulative) peanut protein at week 24	SAF	Descriptive statistics/missing data as non-responder	Descriptive statistics with available week 24 data	Yes	Bar chart
Secondary Endpoints					
Change in the cumulative tolerated dose (log transformed) mg of peanut protein during a DBPCFC from baseline to measured DBPCFC visits at week 24	SAF	Descriptive statistics/LOCF method	Descriptive statistics with available week 24 data	Yes	Bar chart
Change in the cumulative tolerated dose (log transformed) mg of peanut protein during a DBPCFC from baseline to measured DBPCFC visits at week 36	Subset of SAF at week 36	Descriptive statistics	No	No	Bar chart
Proportion of patients treated with dupilumab that pass a DBPCFC with at least 444 mg (cumulative) peanut protein at week 36	Subset of SAF at week 36	Descriptive statistics	No	No	Bar chart
Proportion of patients treated with dupilumab that pass a DBPCFC with at least 1044 mg (cumulative) peanut protein at week 24	SAF	Descriptive statistics/missing data as non-responder	No	Yes	Bar chart

Endpoint	Analysis Populations	Primary Statistical Method	Supportive/Sensitivity Analysis	Subgroup Analysis	Other Analyses
Proportion of patients treated with dupilumab that pass a DBPCFC with at least 1044 mg (cumulative) peanut protein at week 36	Subset of SAF at week 36	Descriptive statistics	No	No	Bar chart
Proportion of patients treated with dupilumab that pass a DBPCFC with 2044 mg (cumulative) peanut protein at week 24	SAF	Descriptive statistics/missing data as non-responder	No	Yes	Bar chart
Proportion of patients treated with dupilumab that pass a DBPCFC with 2044 mg (cumulative) peanut protein at week 36	Subset of SAF at week 36	Descriptive statistics	No	No	Bar chart

Safety Analysis:

Endpoint	Analysis Populations	Primary Statistical Method	Supportive/Sensitivity Analysis	Subgroup Analysis	Other Analyses
Primary Endpoint					
Adverse events	SAF	Descriptive Statistics and time-to- event analysis	No	Yes, for selected AE summary	No
Laboratory measures	SAF	Desriptive Statistics	No	No	No
Vital sign	SAF	Descriptive Statistics	No	No	No
Spirometry	SAF	Descriptive Statistics	No	No	No

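### The 80% power in SAP 2.3 belongs to a chi-square test in 20 evaluable patients; the planned Clopper-Pearson analysis at N = 24, read against 8%, has about 56% to 74%

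*SAP*

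**What the plan says.** **Sample size.** SAP 2.3 states: "A sample size of 20 patients will have 80% power to detect the 21% difference in tolerated rate at the 2-sided 5% significance level". The assumed pass rates are 29% on dupilumab and 8% as reference, and the method named is a one-sample chi-square test with normal approximation. Protocol 11.2 has the same calculation and continues: "Allowing for a dropout rate of around 15%, approximately 24 patients will be required". SAP 2.3 repeats that step.

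**Hypothesis.** SAP 2.2 sets the null at 8% and says: "The following hypothesis will be tested at the 2-sided 5% significance level".

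**Primary analysis.** Protocol 11.4.3.1 plans a one-sample chi-square test. SAP 1.2.3 makes the analysis descriptive and drops the p-value. SAP 5.6.1 then says: "Estimate of proportion and the 2-sided 95% Clopper-Pearson confidence interval will be provided". SAP 3.1 analyses efficacy in every patient who received dupilumab.

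**Missing week 24 challenges.**
- Protocol 11.4.3.1: "the patient will be considered as a non-responder regardless of reasons for missing data".
- SAP 5.6.1 restricts this: if the challenge is missing "due to reasons not related to COVID-19, the patient will be considered as a non-responder at week 24". Results missing because of COVID-19 are multiply imputed.
- The SAP 10.1 table lists only "Descriptive statistics/missing data as non-responder" and does not mention the COVID-19 rule.
- Only the supportive analysis is confined to patients with data: "Supportive analysis of the primary endpoint will include an analysis of patients who have available week 24 DBPCFC of peanut protein".

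**The concern.** There are three mismatches.

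1. **Denominator.** Going from 20 to 24 treats dropouts as leaving the analysis. The primary analysis keeps them, and all but the COVID-19 cases count as failures. A denominator of 20 evaluable patients fits only the supportive analysis.
2. **Method.** The power is for a chi-square test that the SAP has withdrawn. No power or precision is given for the interval that replaces it.
3. **Reading.** SAP 2.2 still announces a test at the two-sided 5% level, SAP 1.2.3 removes it, and nothing says how the interval is to be compared with 8%.

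A reader will take it that the trial had an 80% chance of showing a rate above 8%, and the planned analysis does not have that at N = 24. The reading could also be chosen after the data are seen, because the chi-square test and the interval can give opposite answers on the same count. The estimate, the interval and the responder rule are not themselves wrong.

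**Working it through.** **Inputs.** Reference rate p0 = 0.08 and two-sided 5% level (SAP 2.2). Assumed rate p1 = 0.29, n = 20, dropout about 15%, N about 24 (SAP 2.3, Protocol 11.2). Clopper-Pearson interval and missing-data rules (SAP 5.6.1).

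**Step 1: reproduce the plan's figure.** One-sample test, null variance under the null and alternative variance under the alternative:

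- n for 80% = [(1.960·√(0.08·0.92) + 0.842·√(0.29·0.71)) / 0.21]² = 18.9
- power at n = 20 = Φ[(0.21 − 1.960·√(0.08·0.92/20)) / √(0.29·0.71/20)] = Φ[(0.21 − 1.960·0.0607)/0.1015] = 81.5%
- 20/0.85 = 23.5, rounded up to 24

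So the stated figures hold for the stated method.

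**Step 2: passes needed at N = 24.**

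| Passes | Chi-square z, p | 95% Clopper-Pearson |
|---|---|---|
| 4/24 | 1.565, 0.118 | not needed |
| 5/24 | 2.317, 0.020 | 7.1% to 42.2% |
| 6/24 | not needed | 9.8% to 46.7% |
| 7/24 | not needed | 12.6% to 51.1% |

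The chi-square test rejects 8% from 5/24. The Clopper-Pearson lower limit first exceeds 8% at 6/24.

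**Step 3: effective pass rate.** If 29% is the rate among those challenged and a 15% dropout counts wholly as failure, the rate over all treated patients is 0.85 × 0.29 = 0.2465. If there is no dropout, or if 29% already counts dropouts as failures, it is 0.29. If a share s of the missing results is due to COVID-19 and the imputed results are treated as observed, it is 0.29 × (0.85 + 0.15s).

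**Step 4: exact binomial power at N = 24.**

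| Case | Rate | Interval: P(X ≥ 6) | Chi-square: P(X ≥ 5) |
|---|---|---|---|
| 15% dropout, all failures | 0.2465 | 56.2% | 74.1% |
| s = 25% | 0.2574 | 61.0% | not needed |
| s = 50% | 0.2683 | 65.6% | not needed |
| s = 75% | 0.2791 | 69.8% | not needed |
| No dropout, or 29% already net of it | 0.29 | 73.8% | 86.8% |

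The difference between the last two columns is the chance of exactly 5 passes, where the readings conflict: 86.8% − 73.8% = 13.0% at a rate of 0.29, and 74.1% − 56.2% = 17.9% at 0.2465.

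**Step 5: sensitivity to N.** N is approximate and exact power moves in steps. The interval needs 5 passes at N = 21 and 6 at N = 22 to 26.

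| N | 21 | 22 | 23 | 24 | 25 | 26 |
|---|---|---|---|---|---|---|
| No dropout | 77.3% | 64.9% | 69.6% | 73.8% | 77.6% | 80.9% |
| 15% as failures | 61.9% | 46.8% | 51.6% | 56.2% | 60.6% | 64.8% |

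**The case against.** The strongest reply is that nothing has been miscalculated. The sample-size section names its test, and its figure reproduces. The SAP openly made the analysis descriptive, so there is no success criterion, and power against 8% exists only once a rule is supplied from outside. The low end also needs 29% to be the rate among challenged patients and no missing result to be due to COVID-19. The documents do not settle what 29% refers to. If it already counts dropouts as failures, taking off 15% again counts them twice, and the protocol's chi-square test then has 86.8% at N = 24. Part of the gap reflects how conservative the exact interval is: requiring 6/24 has an upper-tail error of 1.0% at a true rate of 8%, against 3.9% for 5/24.

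Most of this stands as qualification. The 80% is not an arithmetic slip, the rule is assumed, and 56% is the low end of a range. The COVID-19 rows are approximate: 15% of 24 is only 3.6 patients, and pooling imputed datasets by Rubin's formula does not itself yield a Clopper-Pearson interval.

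The objection does not remove the inconsistency. If the analysis is purely descriptive, SAP 2.2 should not announce a test, and SAP 2.3 should give precision. If 8% is still a benchmark, the power should be that of the planned interval, which is below 80% at N = 24 in every case in Step 4.

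**Conclusion.** The concern holds. The 80% is right for a chi-square test in 20 evaluable patients, but it does not belong to the primary analysis in SAP 5.6.1. Read against 8%, that analysis has about 56% to 74% power at N = 24. The range assumes that 8% counts as excluded when the lower Clopper-Pearson limit exceeds it, that the true rate is 29%, and that dropout is between nil and 15% and unrelated to outcome. The top of the range also applies if 29% already counts dropouts as failures. The intermediate values for COVID-19 missingness are slightly optimistic because imputed results are treated as observed.

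The denominator mismatch alone matters for the protocol's own test: 74.1% with 15% counted as failures, against 86.8% with no dropout or with 29% already net of it. The protocol's 80% therefore holds on the second reading only. This should be fixed, but it does not undermine the estimate or its interval.

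**What to change.** - **SAP 2.3:** keep the 80% only as the original planning calculation. Add either the 56% to 74% range at N = 24 with its assumptions, or the expected precision, for example 7/24 = 29.2% with a 95% interval of 12.6% to 51.1%.
- **SAP 2.2 and 5.6.1:** either state one rule (8% is excluded if the lower 95% Clopper-Pearson limit exceeds 8%, which means at least 6/24) or delete the sentence that says the hypothesis will be tested.
- **Protocol 11.2, or SAP 1.2.3 if no amendment is opened:** say that chi-square power at 24 is about 74% with a 15% dropout counted as failures and about 87% with none.
- **SAP 10.1:** bring the missing-data entry into line with the COVID-19 rule in 5.6.1.

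The cost is wording only, with no extra patients and no new estimator. The drawback is that the stated figure becomes less favourable.
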